6.4.3 Schedule of Assessment

Assessment	Screening/ pre-admission	Randomisation	Treatment/ Procedure	Implant	Recovery	6 weeks (telephone)	3 month (clinic)	12 month /EOS (clinic)	Monthly downloads	Registry
Visit window	-14 days	Day 0	Day 0	Day 0		42 days +/- 3 days	+/ - 7 days	+/ - 2 weeks		
Informed consent	X									
Patient baseline characteristics recorded: estimated AF duration, LA dimensions (echo), LVEF, Bloods, Medications, Age, Sex, BP, CHADS VASC score, comorbidities, demographics, weight, height, BMI.	X									
Randomisation		X								
DCCV only			X							
DCCV plus Pulmonary Vein Isolation			X							
Telephone FU						X				
Quality of life measures	X					X	X	X		
Clinical FU						X	X	X		
Loop recorder inserted				X						
12 lead ECG					X		X	X		
Interrogation of loop recorder				X			X	X	X	
Symptom questionnaires	X					X	X	X		
Clinical status and mortality data										X

6.4.4 Assessment of feasibility endpoints

Protocol non-adherence is defined as the proportion of patients in each randomised group who undergo the treatment that they were not randomised to as part of the index procedure, i.e. those randomised to DCCV only undergoing DCCV plus PVI, and those randomised to the DCCV plus PVI group who only undergo DCCV as part of the index trial procedure.

Recruitment rate will be defined as the total number of patients recruited divided by the number of months during which recruitment takes place.

Loss to follow-up will be defined as a) the number lost to follow-up at 12 months as a proportion of the number randomised. b) the number who do not consent to the collection of 5-year registry data as a proportion of the number randomised.

Data completeness will be defined as the number of subjects completing each assessment as a proportion of the total randomised. For this pilot study, analyses will be conducted on a complete case basis, and the level of missing data will be assessed to help inform as to best methods to use to handle potential missing data within a larger future trial.

Blinding index will be assessed as described by Bang et al (BI)². Patients and staff will be asked to guess the treatment allocation and will answer DCCV, DCCV+PCI, or don't know. The BI is scaled to an interval of -1 to 1 with 1 being complete lack of blinding, 0 being perfect blinding and -1 indicating opposite guessing.

Other feasibility endpoints including assessing study logistics, identifying barriers and facilitators to implementation, and assessing the acceptability of the interventions will be assessed qualitatively, and hence will not be described further in the SAP.

6.4.5 Assessment of primary and secondary efficacy endpoints

The primary endpoint is defined as the proportion of randomised patients with recurrent AF (AF episode lasting > 7 days) within 12 months, but outside of the initial 6-week blanking period (see section 8.1.2).

Secondary endpoints to be described are:

- Proportion dying within 12 months
- Proportion with hospital admission for any reason within 12 months
- Proportion with procedural-related complications defined as any AE that is deemed at least possibly related to intervention
- Proportion with bleeding events within 7 days of procedure
- Proportion with repeat procedures (any additional procedure for AF after the baseline index trial procedure(s)) within 12 months
- Change in ejection fraction from baseline at 12 months
- Proportion with clinical success of procedure
- Change in QoL at 12 months, as measured by SF-12 and AF-PROMS
- AF burden by 12 months
- Anti-arrhythmic drug use.

Clinical success will be defined as a 75% or greater reduction in the number of AF episodes as measured by the Reveal LINQ implant device within 12 months, but outside of the initial 6-week blanking period.

Change in QOL will be measured by the change in AF-PROMS summary scores and SF-12 PCS and MCS between screening and 12 months. SF-12 scores will be calculated as described in the appendix supplementary table 2³.

AF burden will be defined as the proportion of time in AF over the 12 months but outside of the initial 6-week blanking period, as measured by the Reveal LINQ implant device.

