	
months to set up, 3 months to recruit, treatment (1 day), 3 month follow up and 2 months study closure. For the larger trial in 4-5 UK centres: Set-up 6 months, 6 month recruitment, treatment (1 day), 12 month follow-up, 3 months study closure.

--	---

5. Introduction

Patients with persistent atrial fibrillation undergoing catheter ablation are reported to have fewer symptoms and better quality of life than those undergoing DC cardioversion (DCCV) or optimal medical therapy. However, as yet this has not been subjected to a randomised, prospective, blinded clinical trial (January et al., 2014).

Atrial fibrillation (AF) is the commonest cardiac arrhythmia, with a prevalence of 5.5% (Heeringa et al., 2006). A major cause of the life-changing complication of stroke, AF is associated with severe symptoms, such as palpitations, shortness of breath, lethargy and a reduced quality of life. AF can be classified into paroxysmal, persistent or long-standing persistent. Paroxysmal AF refers to when episodes last less than 7 days before spontaneously termination, persistent AF implies episodes lasting greater than 7 days or requiring either electrical or pharmacological cardioversion, and longstanding persistent AF describes AF episodes lasting more than one year in duration trial (January et al., 2014).

Patients differ widely in the diversity and severity of their AF symptoms. Some 15-30% of patients with AF are asymptomatic. Data from implantable cardioverter-defibrillators (ICDs) and pacemakers have demonstrated that up to 70% of paroxysms of AF are asymptomatic. There is a need to clarify the relationship between patient reported symptoms and the arrhythmia itself. It is likely that both somatic and psychological factors contribute to this relationship. Patient perception or awareness of symptoms is often not a good discriminator of the severity of the arrhythmia. In the present study we will also collect information from patients on reported symptoms and effects on quality of life (both physical and mental), functional status and treatment satisfaction. We will be able to look at these and assess the correlations between reported symptoms and arrhythmia as captured by the LINQ device.

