6.3 Primary endpoint

- Recurrence of Persistent AF (AF episode lasting > 7 days).

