7.1 Inclusion criteria

Patients who meet the following inclusion criteria will be eligible for the study;

- Ability to give informed consent
- Age 18-80 years
- Persistent AF (atrial fibrillation lasting > 7days) of total continuous duration <2 years as documented in medical notes.
- Patients being considered for cardioversion.

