There is a benefit to participants in the study in having the implantable cardiac device which will monitor their heart allowing immediate knowledge if their heart rhythm goes back into AF. Otherwise there are no further individual benefits in participating in the study.

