6.4 Efficacy Endpoints

6.4.1 Primary endpoint

- Recurrence of Persistent AF (AF episode lasting > 7 days) within 12 months.

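### The primary endpoint counts only AF episodes longer than 7 days, so a post-blanking relapse ended by cardioversion or repeat ablation by day 7 can be scored as no recurrence

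*SAP*

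**What the plan says.** The primary endpoint is set by duration alone wherever it is defined. SAP 6.4.1 lists "Recurrence of Persistent AF (AF episode lasting > 7 days) within 12 months". Protocol 6.3 uses the same 7-day threshold without the time limit. SAP 6.4.5 turns it into the proportion of randomised patients "with recurrent AF (AF episode lasting > 7 days) within 12 months" and removes the first 6 weeks as a blanking period. The corresponding row of SAP Table 4 is labelled as recurrent AF within 12 months and states no duration.

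The protocol's introduction (section 5) is wider. There, "persistent AF implies episodes lasting greater than 7 days or requiring either electrical or pharmacological cardioversion". The entry criterion in Protocol 7.1 goes back to duration only: "Persistent AF (atrial fibrillation lasting > 7days) of total continuous duration <2 years as documented in medical notes".

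Re-treatment of a relapse appears only among the secondary endpoints. SAP 6.4.5 counts repeat procedures, meaning any further AF procedure after the index one within 12 months, and also AF burden and antiarrhythmic drug use. SAP 7.2.1 analyses every randomised patient in the assigned group. In the text available, nothing treats a cardioversion or repeat ablation as a primary event, censors at it, or otherwise says how it affects the primary endpoint. Nor does anything prevent one from taking place before day 7 of a relapse.

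**The concern.** Consider a patient who relapses in month 5, is cardioverted on day 3 of the episode, and has no later episode over 7 days. Under the introduction's classification this was persistent AF. Under SAP 6.4.5 it is not an event, and the patient stays in the denominator as recurrence-free. The re-treatment has removed the outcome that it was a response to.

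The primary endpoint would then depend partly on how quickly relapses are re-treated and not only on whether they occur. The pilot tests no hypothesis (SAP 6.5), but in an arm of 10 one such patient moves the proportion by 10 points. The definition also matters later: SAP 6.1 includes pilot patients in the main trial if that trial is feasible and the design has not changed in a major way. Protocol 11.2 lists the assessment of outcome measures among the progression criteria, so the pilot is the natural time to settle the rule.

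**Working it through.** **Step 1. How one relapse is scored.** Take a relapse that starts after week 6, is ended on or before day 7, and is not followed by a longer episode.

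| Rule | Ended by electrical cardioversion or ablation | Ended by a drug |
|---|---|---|
| Protocol 5 classification | Persistent if it required cardioversion; ablation is not named | Persistent if it required cardioversion |
| Protocol 6.3, SAP 6.4.1, SAP 6.4.5 | No event | No event |
| SAP 6.4.5 repeat procedures | Counted | Not clearly counted |
| SAP 6.4.5 drug use and AF burden | Burden only | Both, without attribution |

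The scoring gap follows from the wording alone and needs no arithmetic.

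**Step 2. Reproduce the planning figures.** Protocol 11.1 gives 12-month recurrence of 66% (DCCV) and 47% (ablation), a hazard ratio of 1.7, 80% power, 5% significance and 104 per group.

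- Hazard ratio: ln(1 − 0.66) / ln(1 − 0.47) = 1.70.
- Freedman's formula, two-sided 5%, 80% power: 117 events.
- Mean event probability: (0.66 + 0.47) / 2 = 0.565.
- Per group: 117 / 0.565 / 2 = 103.5, so 104.

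The stated figure reproduces and is not in dispute.

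**Step 3. Illustrate the effect of missed events.** Let f be the share of recurrences ended by treatment by day 7 with no later episode over 7 days. The documents give no value for f, so 10% to 30% is an assumption. Each arm's rate becomes p × (1 − f), and the hazard ratio is ln(1 − DCCV rate) / ln(1 − ablation rate). Power is by Schoenfeld's formula at 104 per group.

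| f, both arms | DCCV | Ablation | Difference (points) | Hazard ratio | Power |
|---|---|---|---|---|---|
| 0% | 66.0% | 47.0% | 19.0 | 1.70 | 0.82 |
| 10% | 59.4% | 42.3% | 17.1 | 1.64 | 0.72 |
| 20% | 52.8% | 37.6% | 15.2 | 1.59 | 0.62 |
| 30% | 46.2% | 32.9% | 13.3 | 1.55 | 0.52 |

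With equal f the risk ratio does not move: 0.47 / 0.66 = 0.712 in every row. What is lost is absolute difference, events and power.

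**Step 4. Check the direction.** At f = 20% in one arm only:

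- DCCV arm only: 52.8% v 47.0%, hazard ratio 1.18.
- Ablation arm only: 66.0% v 37.6%, hazard ratio 2.29.

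The sign of the bias depends on where the early re-treatment falls, and the documents do not say.

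**Step 5. How likely is early re-treatment?** Protocol 9.7 specifies monthly remote interrogation. If onset is uniform over a 30-day interval (an assumption), about 7/30 = 23% of episodes would be downloaded within 7 days of onset, before any procedure could be arranged. Patients are blinded to their ECG and rhythm (Protocol 9.3.1). The re-treatment route in Protocol 12.3.1 is for patients who have gone back into persistent AF, which on the 7-day definition is usually after the event has been counted. Presentation with symptoms remains possible.

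**The case against.** The best defence is that this is a deliberate and consistent choice. The wider definition is background classification; the entry criterion, the protocol endpoint, the SAP endpoint and the SAP's description of participants (section 8) all use the 7-day threshold. A reader might infer that protocol and SAP contradict each other on the primary endpoint. They do not: the mismatch is between the introduction and the endpoint, and it is not explained.

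A reader might also take Protocol 12.2, which describes the implant as "allowing immediate knowledge if their heart rhythm goes back into AF", to mean that early re-treatment will be common. That is a statement of benefit to participants, and the operational text in step 5 points the other way.

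Nor do the documents support the inference that the gap must shrink the treatment difference, or that it acts mainly in the DCCV arm. Step 4 shows that it can go either way. Ward staff are told to manage every patient as if ablated (Protocol 9.6) and other healthcare professionals are blinded (Protocol 9.3.4), so re-treatment confined to one arm is unlikely while blinding holds.

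Finally, repeat procedures and AF burden are reported beside the primary endpoint, and having no episode over 7 days while also having a repeat procedure is not contradictory. This stands, but Table 4 gives totals by arm and does not link the two rows within a patient, and the primary proportion still counts that patient as recurrence-free.

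**Conclusion.** The gap is real and modest. As written, a post-blanking relapse ended by electrical cardioversion or repeat ablation by day 7, with no longer episode afterwards, is scored as no recurrence, and neither document says that this is intended. The frequency and the direction of any bias are unknown, and the operational text suggests that such cases are uncommon. The reduction from 19 to 17.1, 15.2 or 13.3 points is an illustration that rests on an assumed equal f of 10%, 20% or 30%; it is not an estimate. It also assumes that the 47% and 66% planning rates include relapses that were cardioverted early, which the documents do not state. On that assumption, counting these relapses leaves the 104 per group unchanged. The case for a change is that it is cheap and removes a dependence of the outcome on re-treatment, not that a large bias has been shown.

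**What to change.** In SAP 6.4.1, SAP 6.4.5, Table 4 and Protocol 6.3:

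- Score as an event the first AF episode after the blanking period that lasts more than 7 days, or during which an electrical cardioversion or repeat ablation for AF is performed. Date the procedure from the repeat-procedure records.
- Report the duration-only loop-recorder definition as a sensitivity line in Table 4.
- Leave termination by drugs to the antiarrhythmic-use and AF-burden endpoints unless an attribution rule is specified in advance. Protocol 16.5 leaves drug choice to the physician, and neither document gives a way to tell drug-related from spontaneous termination.
- Reconcile the definition in Protocol 5 with the endpoint wording, with a sentence explaining any difference that remains. Counting repeat ablation goes slightly beyond Protocol 5, so say so.

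The cost is wording in two documents and matching procedure dates to device episodes, both of which are already collected. The downside is that the event is no longer purely device-derived: it includes a clinician's decision, though one made blinded to allocation while blinding holds. The change concerns outcome scoring only and alters no treatment rule.

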6.1 Design

ORBITA-AF feasibility study is an internal pilot study. It is a randomised blinded controlled trial at two sites. Patients will be randomised to receive DCCV+PVI or DCCV alone. No information about the procedure will be transferred from catheterisation laboratory (cath lab) staff to recovery staff and cath lab staff will have no further contact with the patient during the study. Patients and other healthcare professionals will remain blinded to treatment allocation. If a future trial is determined to be feasible and no major changes to the design have been made from this pilot study, then pilot study patients will be included in the future main trial. This pilot study aims to recruit 20 patients.

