6.5 Level of significance

No hypothesis testing will be done for this pilot study.

For efficacy outcome measures we will use 80% one-sided confidence intervals to give an indication of whether the endpoint is likely to be of interest, an approach described by Cocks et al. for pilot trials⁴.

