7.1 Study period and visit definitions

7.1.1 Visits

Patients will be identified as suitable for the study by their usual clinical care provider. Patients referred for DC cardioversion or management of persistent AF will be screened for inclusion into the trial. Patients will give informed consent in pre-admission. Baseline characteristics, quality of life and symptom measures will be assessed at this point.

On the day of the procedure patients will be randomised to DCCV or Pulmonary Vein Isolation plus DCCV. LINQ will be inserted during the procedure. Patients will be followed up at 6 weeks by telephone for quality of life and symptom measures.

Patients will return to the clinic at 3 months (clinical follow-up, 12 lead ECG, repeat QOL and symptom measures) and at 12 months (clinical follow-up, 12 lead ECG and symptoms). Monthly remote interrogation of the loop recorder will measure burden of AF (time in AF) and duration of episodes.

[figure not shown]
Patients who consent will remain within an observational registry for 5 years following the end of the trial. This long-term passive follow-up will track patient mortality and clinical status from

ORBITA-AF Pilot Trial: Statistical Analysis Plan

routinely collected clinical data. No intervention or investigations will be performed as part of this long term follow up.

Data from this pilot study will be analysed at 12 months to allow assessment of feasibility for a larger trial, and patients who complete the 12-month follow-up visit and consent will continue in registry follow-up for 5 years post procedure.

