7.4 Treatment assignment and treatment groups

Patients will be randomised on a 1:1 basis to either DCCV alone or DCCV + PVI. Block randomisation is used with randomly varying block sizes of length 2, 4, and 6. Randomisation will not be stratified by any factors. The allocation algorithm is written by the study statistician using R (randomizeR package). Details of the randomisation method and validation details are stored in a separate document which can be accessed by the trial statistician and the database manager.

The randomisation list will then be uploaded to the study database (REDCap). When a patient has been screened and has met all of the entry criteria in order to be eligible for trial participation, the unblinded investigator will go to the randomisation module on the database and complete the randomisation form. Once complete, the allocation (which is next in the sequence on the randomisation list) will be revealed to the unblinded investigator.

8 Patient Disposition

Participants will be those referred for either cardioversion for persistent AF (> 7 days) or catheter ablation of persistent AF. Inclusion/exclusion criteria are detailed in the protocol (section 7). Numbers of patients screened, excluded prior to randomisation by reason and overall, randomised and completing each phase of the study will be shown by treatment groups and overall following the Consort structure.

9 Demographics and Baseline characteristics

Demographic and baseline (screening data) will be:

1. Age
2. Sex
3. Ethnicity

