DCCV + PCI	n12 (p12)	n22 (p22)	-
Don't know	n13 (p13)	n23 (p23)	-
Total	N1	N2	-
Blinding index	BI	BI	-

Table 3: Data completeness

	Treatment group		Total
	DCCV (N=)	DCCV +PVI (N=)	
Primary Endpoint data (Persistent AF)	N1 N2 % with data	N1 N2 % with data	N1 N2 % with data
SF12 3 months	N1 N2 % with data	N1 N2 % with data	N1 N2 % with data
12 months	N1 N2 % missing	N1 N2 % missing	N1 N2 % with data
AF-PROMS 3 months	N1 N2 % with data	N1 N2 % with data	N1 N2 % with data
12 months	N1 N2 % with data	N1 N2 % with data	N1 N2 % with data
Loop recorder interrogation performed			
3 months	N1 N2 % with data	N1 N2 % with data	N1 N2 % with data
12 Months	N1 N2 % with data	N1 N2 % with data	N1 N2 % with data
Patients completing all study assessments	N1 N2 % with data	N1 N2 % with data	N1 N2 % with data

N1= Number with data recorded

N2=Number with missing data

Table 4: Primary and Secondary Efficacy Endpoint analysis (ITT population)

	Treatment group		OR (80% CI)
	Placebo N=	Active N=	
Recurrent AF within 12 months	n/N (%)	n/N (%)	
Death within 12 months	n/N (%)	n/N (%)	
Hospital admission within 12 months	n/N (%)	n/N (%)	
Procedural-related complications	n/N (%)	n/N (%)	
Bleeding events within 7 days	n/N (%)	n/N (%)	
Requirement for repeat procedures within 12 months	n/N (%)	n/N (%)	
Clinical success of procedure	n/N (%)	n/N (%)	
AF drug use within 12 months	n/N (%)	n/N (%)	
	Placebo N=	Active N=	b (80% CI)
Change in ejection fraction at 12 months	Mean (SD)	Mean (SD)	
AF-Burden	Median [IQR] N Mean (SD)	Median [IQR] N Mean (SD)	
Change in QoL score at 12 months: SF-12 MCS	Mean (SD) N	Mean (SD) N	
SF-12 PCS	Mean (SD) N	Mean (SD) N	
AF-PROMS	Mean (SD) N	Mean (SD) N	

Table 5: Safety analysis – adverse events (safety population)

		Treatment group	
		Placebo N=	Active N=
Number of patients experiencing an AE within a year		n/N (%)	n/N (%)
Maximum severity AE experienced	Mild	n/N (%)	n/N (%)
	Moderate	n/N (%)	n/N (%)
	Severe	n/N (%)	n/N (%)
Total number of AEs across patients		n	n

Table 6: SAE listing

SAE number	Patient ID	SAE term (MedDRA)	SAE severity	Expected/ unexpected	Treatment group	Details of treatment	Related to treatment?
1							
2							
3							
4							
...							

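### The 75% reduction that defines clinical success has no measured pre-procedure reference, so its Table 4 row needs an imputation that the SAP does not state

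*SAP*

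**What the plan says.** SAP 6.4.5 gives the rule: "Clinical success will be defined as a 75% or greater reduction in the number of AF episodes as measured by the Reveal LINQ" implant, within 12 months and outside the first 6 weeks. It does not say what the reduction is measured from. The other change endpoints in the same section do name a reference: baseline for ejection fraction, and screening for quality of life.

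On device timing, SAP 7.1.1 says "LINQ will be inserted during the procedure". The row "Loop recorder inserted" in the SAP 6.4.3 schedule is marked under Implant, which is Day 0. Protocol sections 8, 9.3.2, 9.3.3, 16.2.1 and 16.2.2 agree.

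The list in SAP Section 9 that opens "Demographic and baseline (screening data) will be" includes AF duration but no count of AF episodes and no burden. The one burden measure is a follow-up measure: "AF burden will be defined as the proportion of time in AF over the 12 months but outside of the initial 6-week blanking period".

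Table 4 in SAP Section 13 nevertheless carries the row "Clinical success of procedure", with n/N (%) by arm and an odds ratio with an 80% interval.

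**The concern.** The rule compares a follow-up count with an earlier count from the same device, but the device is not in place before treatment. The only LINQ data outside the endpoint window come from the 42 blanking days. Those days follow treatment and are themselves excluded, so they cannot serve as the reference.

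Two outcomes are possible. The row is left blank, or the analyst supplies a starting value that the SAP does not state. If that value is chosen after outcomes are known, the choice is post hoc, and it feeds an odds ratio that SAP 6.5 uses to indicate whether an endpoint is likely to be of interest. The definition could also pass unchanged into the main trial: SAP 6.1 says that, if a future trial is feasible and the design has no major change, "then pilot study patients will be included in the future main trial".

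**Working it through.** The plan states no figure for this endpoint, so there is none to reproduce. The check asks whether the terms of the rule are collected, and then whether the choice of substitute matters.

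**Step 1. The rule as a formula.** Let F be the LINQ episode count within 12 months outside blanking, and B the pre-procedure count. Reduction = 1 − F/B. Success requires 1 − F/B ≥ 0.75, that is, F ≤ 0.25 × B.

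**Step 2. What is collected.**

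| Term | Source in the SAP | Available? |
|---|---|---|
| F | LINQ interrogations at 3 and 12 months and monthly downloads (6.4.3) | Yes |
| B | Implant and first interrogation both on Day 0 (6.4.3, 7.1.1) | No |
| Substitute for B | Screening data (6.4.3, Section 9): AF duration only | No count, no burden |

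B is missing by design for every patient, so 1 − F/B has no measured denominator.

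**Step 3. Imputing a count.** Suppose entry is treated as B episodes (an assumption; neither document gives B). The largest F that still counts as success is the whole-number part of 0.25 × B:

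| Assumed B | 0.25 × B | Largest F for success |
|---|---|---|
| 1 | 0.25 | 0 |
| 2 | 0.50 | 0 |
| 3 | 0.75 | 0 |
| 4 | 1.00 | 1 |
| 8 | 2.00 | 2 |

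With B = 1 (one continuous episode at entry), success means no LINQ episode of any length after blanking.

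**Step 4. Imputing a burden.** Suppose entry burden is taken as 100% (again an assumption). A 75% reduction then means follow-up burden of 25% or less.
- Days outside blanking: 365 − 42 = 323, which is 323 × 24 = 7,752 hours.
- Threshold: 0.25 × 323 = 80.75 days.

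**Step 5. The same hypothetical patients under both imputations**, each with full follow-up and no other AF:

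| AF after blanking | B = 1: reduction | Result | Burden | Result at 25% |
|---|---|---|---|---|
| None | 1 − 0/1 = 100% | Success | 0% | Success |
| One 2-hour episode | 1 − 1/1 = 0% | Failure | 2/7,752 = 0.03% | Success |
| One 80-day episode | 0% | Failure | 80/323 = 24.8% | Success |
| One 81-day episode | 0% | Failure | 81/323 = 25.1% | Failure |

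The two imputations disagree for any patient whose only AF after blanking is one episode of up to 80 days.

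**The case against.** The strongest reply is that the reference is implied. Protocol 7.1 admits only patients in continuous persistent AF documented in their notes, so entry could be read as one ongoing episode, or as a burden of 100%. This shows that the row can be filled once a rule is chosen, and to that extent it stands. A reader might infer that the endpoint is beyond rescue for all 20 patients and the row must stay empty. The documents do not support that. What they do show is that no rule is stated, and Step 5 shows that the two natural rules give different answers.

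A second reply is that Protocol 16.1 puts the device in at the preadmission clinic, which would give some earlier recording. No other section says this; the SAP and five other Protocol sections contradict it, and neither schedule has an interrogation before the procedure. Even if it were followed, the SAP screening window allows at most about 14 days against 323, a ratio of 323/14 ≈ 23, with no standardisation to a rate.

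A third reply is that Protocol 6.4 also allows a reduction in percentage of time in AF. SAP 6.4.5 does not carry that form over, and it too lacks a starting value. The SAP cites Protocol version 2.0 of 25/06/2019, whereas the supplied Protocol is signed 12 February 2019, so its wording may have changed. The conflict lies within the SAP and does not depend on the version.

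The last reply concerns weight, and most of it stands. SAP 6.5 says "No hypothesis testing will be done for this pilot study", the pilot exists partly to assess outcome measures, and continuous LINQ data would still allow a threshold to be applied later. It is also fair that a 25% rule is a choice and that deleting the row would be enough.

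**Conclusion.** The point holds. Clinical success, one of eight odds-ratio rows in Table 4, cannot be calculated from the data that the SAP collects without an unstated imputation, and the choice of imputation changes who counts as a success. This is more than missing detail, because the design never collects the quantity that the rule needs.

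The reach is narrow: one descriptive secondary endpoint in a 20-patient pilot. A reader might infer that the LINQ-based results in general are in doubt. They are not. The primary endpoint (an AF episode lasting more than 7 days) and AF burden are both defined on follow-up data alone and need no pre-procedure value.

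The absence of a reference rests on the SAP text and needs no assumption. The worked comparison assumes a 365-day year, full follow-up and the two imputed baselines. The 100% figure cannot be checked from scheduled data. Protocol 16.5 encourages antiarrhythmic drugs such as amiodarone from at least 2 weeks before the procedure, so some patients may be in sinus rhythm by Day 0, and the schedule lists a 12-lead ECG only at recovery, 3 months and 12 months.

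**What to change.** Before unblinded 12-month data are seen, do one of the following.

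- **Replace the sentence in SAP 6.4.5** with: *Clinical success is a LINQ AF burden of 25% or less over the 12 months outside the initial 6-week blanking period. This is equivalent to a 75% reduction from a pre-procedure burden that is assumed, not measured, to be 100% under the persistent-AF eligibility criterion.*
- **Or delete the clinical-success row** and report AF burden alone.

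Either is a small SAP edit and needs no new data, because burden outside blanking is already defined and collected.

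The first option has two costs. The endpoint becomes a yes/no cut of the AF burden already in Table 4, on an assumed baseline. And a patient with a single post-blanking episode of about 8 to 80 days would count both as a primary-endpoint recurrence and as a clinical success. If that overlap is unacceptable clinically, deletion is the cleaner choice.
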